TITLE: A Randomized Controlled Trial of Exercise to Reduce Cancer Related Fatigue in Women Undergoing Radiation Treatment for Breast Cancer

PROTOCOL #: Pro2016-XXXX

STUDY DRUG: N/A

IND #: N/A

SPONSOR: Hackensack University Medical Center

PRINCIPAL INVESTIGATOR: [name].
Lombardi Comprehensive Cancer Center
[name]., Ph.D.
Hackensack University Medical Center

ORIGINAL

PROTOCOL VERSION: Version 1.0 – 15 Feb 2016

A Randomized Controlled Trial of Exercise to Reduce Cancer Related Fatigue in Women Undergoing Radiation Treatment for Breast Cancer

[name]., Ph.D. (HUMC)
[name]. (HUMC)
[name]. (HUMC)
[name]. (HUMC)
[name]. (HUMC)

[name]. (LCCC)
[name]. (LCCC)
[name]., Ph.D. (LCCC)

b. ABSTRACT

Cancer related fatigue (CRF) is a common and debilitating side effect of radiotherapy in breast cancer patients. Physical activity interventions can attenuate CRF. The proposed study is a randomized, controlled trial (RCT) of exercise of structured moderate-intensity exercise intervention, delivered concurrently with radiotherapy, to reduce CRF and improve health-related quality of life among breast cancer patients. Eighty women with breast cancer scheduled to receive radiation therapy at HUMC will be randomized to one of the two trial arms: 1) a facility-based aerobic exercise utilizing a portable stationary pedal exerciser; or 2) a control group. Intervention arm participants will exercise at the hospital either before or after their radiation treatment. Assessments will be conducted at baseline, 4 weeks into radiation course, and at 4-week follow-up visit. The outcome variables are CRF, biomarkers of inflammation, and health-related quality of life. The study will provide preliminary evidence on whether a short-term moderate-intensity exercise intervention might be effective in reducing CRF in women undergoing radiotherapy for breast cancer, and whether this effect is mediated by inflammation.

c. Specific Aims

The specific aims of this study are: (1) to test the efficacy of a structured, moderate intensity exercise intervention delivered concurrently with radiation therapy (RT) in reducing CRF among breast cancer patients; (2) to provide pilot data on the acceptability and adherence of the exercise intervention on women receiving treatment; and (3) to determine the impact of exercise on serum inflammation markers among women undergoing RT.

d. Background

Radiation therapy (RT) is frequently used in the treatment of early stage breast cancer.¹ Adjuvant RT combined with partial mastectomy or lumpectomy is associated with better outcomes in early stage breast cancer as compared to surgery alone.^{2,3} RT delivered through conventional external beam radiotherapy or more targeted alternatives like intensity modulated RT (IMRT), is a well-established treatment modality for clinically localized cancer.^{4,5} However, RT has side effects associated with decreases in physical functioning and quality of life.

Cancer related fatigue (CRF), defined as “a distressing, persistent, subjective sense of physical, emotional, and/or cognitive tiredness or exhaustion related to cancer or cancer treatment that is not proportional to recent activity and interferes with usual functioning”, is one of the most debilitating side effects of RT.⁶⁻⁹ Nearly all breast cancer patients report fatigue as a consequence of treatment,^{10,11} and RT-related fatigue is reported in up to 80% of patients.^{1,6-8,12,13} Fatigue can limit a patient’s ability to care for herself and can decrease her quality of life.^{10,14} The severity of its occurrence may also impact treatment continuity.^{10,11}

The etiology of RT-CRF is poorly understood.¹⁴⁻¹⁷ Radiation exposure initiates a programmed response of normal tissue towards tissue remodeling, of which inflammation is an important component.¹⁸⁻²⁰ Inflammation has been hypothesized as a potential cause of treatment-related fatigue¹⁴ as inflammatory markers such as cytokines have been positively associated with increases in fatigue during radiation treatment.^{15,21,22} Although biological correlates of fatigue such as cytokine expression have been identified,¹⁴ elevations in individual cytokines are not consistently associated with fatigue and do not fully explain the occurrence of fatigue in patients who are treated with RT.²³

Several studies have found that physical activity may be an effective intervention to enhance QOL in cancer survivors.²⁴⁻²⁶ Physical activity has been reported to decrease fatigue, anxiety, and depression²⁷⁻³¹, and to improve sleep among healthy adults^{30,31}. More than one third of the decline in functional capacity experienced by cancer patients can be attributed to prolonged physical inactivity³². Prolonged physical inactivity and sedentary lifestyle can lead to rapid losses in fitness, energy, and physical functioning³³. Decreased physical activity may also worsen complaints of cancer related fatigue²⁵. Aerobic exercise training has been found to significantly lower levels of fatigue in patients undergoing RT; however, the mechanism underlying this positive effect is unclear^{7,11,34-36}. Despite the uncertainty about the precise contributions of diverse mechanistic pathways and the timing of introducing an exercise regimen, enough evidence exists of the potential utility of increased exercise to warrant further controlled intervention studies.

e. Methods, including statistical analysis

Study Design

This RCT targets women with breast cancer stages 0-IIIA scheduled to receive RT (no T4, N3, or M1 disease). After obtaining written informed consent, participants are randomized either to a structured moderate-intensity aerobic training exercise regimen concurrent with radiotherapy or to a control group. Endpoints are assessed at baseline, 4 weeks into the radiation course, and at the 4-week follow-up visit. In order to minimize loss to follow up, visits coincide with radiation appointments. Participants in the structured exercise group are instructed to use portable stationary pedal exercisers to achieve an exercise goal of 75 minutes/week of moderate-intensity exercise. All exercise sessions are supervised and conducted in the RT facility while patients are waiting for their RT or after their RT. Radiation therapy is typically administered on a five-times-weekly schedule, amounting to 15 minutes of exercise per weekday. Control group participants are asked to maintain their normal physical activity levels.

Eligibility Criteria

Eligibility for the study includes the following parameters: (1) women between the ages of 18 and 75 years; (2) histologically confirmed non-metastatic carcinoma of the breast (*in situ* disease or invasive); (3) radiation therapy naïve; (4) sedentary activity level at baseline, as defined by less than 60 minutes per week of modest physical activity based on 7-day physical activity recall questionnaire (5) ambulatory; (6) negative serum pregnancy test and not planning to become pregnant in the next three months; and (7) able to provide meaningful consent. Patients must have been deemed by their medical oncologist or internist that they “may participate in [this] exercise trial.” The exclusion criteria include the following: (1) younger than 18 or older than 75 years; (2) no histological confirmation of breast cancer; (3) prior breast, chest, or pelvic radiotherapy; (4) concurrent chemotherapy; (5) distant metastases; (6) physical limitations that contraindicate participation in low to moderate intensity exercise; (7) positive pregnancy test; (8) currently engaged in moderate to vigorous physical activity; and (9) psychiatric disorder which would render the participant unable to provide informed consent. Prior to randomization, participants are required to complete a physical activity readiness questionnaire (PAR-Q) that includes questions regarding physical and medical conditions that would preclude safe participation in an exercise program.

Recruitment

Women with breast cancer stages 0-IIIA, who are scheduled to receive radiation therapy, will be recruited from the Department of Radiation Oncology at Hackensack University Medical Center (HUMC) and screened for eligibility by a study coordinator. Study coordinators will complete, in-person, the eligibility checklist (Appendix A) to confirm eligibility. The study coordinators will obtain informed consent (Appendix B), complete baseline and follow-up assessments, including demographic and treatment history, and will make study assignment as below, under "Randomization".

Randomization

Participants will be randomly assigned to structured moderate-intensity aerobic exercise program or to the control group using a block randomization scheme. The study biostatistician ([name].) will generate the computer-based randomization sequence. The intervention assignment is placed in opaque envelopes and delivered to the study coordinator. After completing baseline assessments, eligible participants will be assigned to study arm by a study coordinator who will open the next one of the sequentially-numbered, sealed envelopes.

Intervention

Arm 1: Exercise Intervention Arm

Participants randomized to the exercise intervention will be required to exercise before or after each radiation treatment session, on a five-treatment per week schedule. No special accomodations will be made to open the clinic on weather days or on extra days in the event of machine failure or patient unavailability. The exercise intervention will be administered at the radiation treatment facility in a room allocated for the study. The exercise prescription consists of aerobic training utilizing the portable stationary pedal exerciser (Pedlar) which contains two cycling pedals mounted to a stationary block that allows patients to exercise while sitting. Pedal tension is adjusted to provide desired resistance. Exercise intensity is self-rated by participants, instructed that moderate intensity goal will "make you breathe somewhat harder than normal". Participants may move and position the device to permit comfortable use while sitting in a chair. Participants are required to perform 15 minutes/day of aerobic exercise using the Pedlar device on radiation treatment days; during a standard radiation course, this will typically yield 75 minutes/week of aerobic time. Ten Pedlar devices have been approved for purchase for HUMC Department of Radiation Oncology through the Development Grant. Participants will record their activity on a daily basis on an exercise log (Appendix H).

Arm 2: Control Arm

Control group participants will be told to maintain their current daily activities and exercise habits for the duration of their treatment.

Study retention and adherence

All participants in the study undergo RT as scheduled by their physician. The exercise intervention does not interfere with dose or timeline of RT. No specific requirements are made herein regarding prone or supine positioning, utilization of standard fractionation or hypofractionation, use of cardiac blocking or for utilization or omission of boost phase of radiation. These treatment decisions are completely at the discretion of the treating radiation oncologist. Adherence to the exercise intervention is achieved by offering participants flexibility in scheduling daily exercise, either before or after radiation treatment. Adherence is recorded in daily participation logs. Logs document participant identification, date, and length of time utilizing the Pedlar device. Participant retention efforts include a \$20 gift card incentive at baseline and one follow-up visit.

Assessments

Three assessments: at baseline, at 4-weeks into radiation course and at 4-week follow-up visit, will be assessed (see Table 1 below).

Table 1: Baseline and Follow-up Assessments

Assessment	Screening	Baseline (T0)	4 weeks (T1)	Follow-up visit (T2)
Eligibility (Appendix A)	X			
Informed Consent (Appendix B)	X			
Demographics (Appendix C)	X			
Medical history (Appendix C)	X			
Medications (from MD Consultation Note)	X			
Cancer and Treatment Summary (Appendix D)	X			
Performance Status	X			
Physical activity readiness questionnaire (Appendix C)	X			
Physical activity recall questionnaire (Appendix E)	X			
Blood tests for hematology (Appendix F)		X		
Vital signs and anthropometrics (Appendix G)		X	X	X
FACIT-Fatigue (in Appendix C)		X	X	X
FACT-B HRQOL (in Appendix C)		X	X	X
Inflammation biomarkers (Appendix F)		X	X	X
Adverse events assessments			X	X
Radiation Treatment Summary (by Treating MD)				X

Outcomes

Primary outcomes

CRF will be determined using the Functional Assessment of Chronic Illness Therapy (FACIT-Fatigue) survey instrument. The FACIT is a 13-item subscale developed to identify a finite set of concerns specific to fatigue. The responses to the 13 items on the FACIT-Fatigue questionnaire are each measured on a 4-point likert scale, with score ranging from 0 to 52. The FACIT-Fatigue scale has been validated in patients with cancer and showed excellent internal consistency and reliability. The following biomarkers of inflammation will be assessed at the Hackensack UMC: (1) High sensitivity CRP (hsCRP) - Serum hsCRP will be measured on the Vitros 5,1 FS Chemistry platform via an immunoassay with a reportable range of 0.10 -15.00 mg/L, and intra- and inter-assay CVs of 1.8-4.0%. (2) Serum fibrinogen and (3) Ferritin will be measured using standardized clinical protocols. All assays have intra- and inter-assays coefficient of variations <10%. We will collect CBC data at each blood draw for correlative and explorative purposes.

Secondary Outcomes

Cancer-related healthcare quality of life (HRQOL) among participants in the study will be measured using the Functional Assessment of Cancer Therapy (FACT) system questionnaires. The HRQOL measures four different domains (physical well-being, functional well-being, emotional well-being, and social/family well-being). FACT-B is a breast cancer specific module that will be used to reflect patients' concerns; moreover, they are reliable, reproducible, and have been validated in numerous studies. Higher scores on the FACT questionnaires reflect higher QOL. Post hoc analysis will be performed to associate RT treatment parameters against differences in outcomes, including utilizing the following pre-specified parameters: heart V5, lung V20, utilization of suprACLAVICULAR field (yes/no), utilization of suprACLAVICULAR field with axillary coverage (yes/no). These will potentially be hypothesis-generating and no Bonferroni corrections will be applied.

Sample size Considerations

In this study participants are randomized into two groups: a structured exercise intervention group and a usual care control group. It is expected that there will be two levels of fatigue measurements: at baseline and after the exercise intervention. Our sample size calculation is based on analysis of covariance (ANCOVA) comparing mean fatigue score differences between the two intervention arms at the end of intervention, adjusting for baseline. In our exercise intervention study ([name] et al, unpublished data, mean fatigue scores of 42.53 (SD=9.35) and 37.12 (SD=9.42) were reported for the intervention and control arms, respectively. In the same study, the correlation coefficient between baseline and after intervention fatigue scores was calculated as 0.64. With the above guidelines and a level of significance of $\alpha=0.05$ (two-sided), we will use randomize 40 women/arm to obtain statistical significance between the arms with 90% power for the overall ANCOVA F-ratio.

Statistical analysis

Baseline characteristics will be compared between the two intervention groups using two-sample t-test or Wilcoxon rank-sum test depending on whether the t-test assumptions are satisfied or not. Suitably transformed variables will be used when necessary. Categorical variables will be compared between the two groups using chi-square tests or Fisher's exact test. The major analytical tool for addressing the specific aims of this study is linear mixed modeling for repeated measures. Study endpoints will be measured three times in each participant in the study, and it is expected that measures on the same individual will be correlated. We will also examine whether the variance of repeated measures changes over time. An appropriate correlation structure will be selected depending on whether there is a trend of variance with time or not. For each outcome measure of interest, a linear mixed repeated measures model will be fit to evaluate the main effects of time, study group, and group-by-time interaction. Known confounders and other covariates will be included in the linear mixed models if their individual bivariate associations with both the group variable and outcome are significant at 10% level.

We hypothesize that participants in the intervention group will have lower average fatigue scores compared to the usual care group after the intervention. For Aim 1 and Aim 3, "change scores" will be defined as the difference between baseline score and 4 week, (end of radiation treatment) score. Change scores will be compared between the two groups using t-test or Wilcoxon rank-sum test. An ANCOVA model will be utilized to assess group differences in change scores adjusting for covariates including age. We hypothesize that participants in the structured exercise intervention group will have lower levels of fatigue (Aim 1) and lower levels of inflammatory biomarkers (Aim 3) compared to baseline at follow-up visits as compared to the usual care control group. We hypothesize that there will be at least partial normalization of both the fatigue levels reported and the inflammatory biomarkers to baseline by the 4-week follow-up visit. Linear mixed models as described above will be used to compare fatigue scores and inflammatory biomarkers levels over time across the study groups. For Aim 2, we will report rates of acceptability and adherence at baseline and end of intervention. We will use the binomial test to compare acceptance and adherence rates between the two intervention arms. Baseline and end of intervention acceptability levels evaluated using the Wilcoxon sign-rank test or McNemar's test (or generalized McNemar's test) for numerical and categorized outcomes, respectively.

A Graduate Research Assistant (GRA) will assist with data collection for the survey data. The GRA will collect log data of the women exercising using the Pedlar device. There is an hourly reimbursement for GRA labor without incentive. This has been approved via the Development Grant.

f. Significance

This study will contribute to the literature on the role of concurrent radiation treatment and moderate-intensity exercise in reducing cancer-related fatigue and improving HRQOL among breast cancer patients undergoing.

This study will also provide pilot data on the correlation of inflammatory markers with exercise-related changes in fatigue and other HRQOL measures in breast cancer patients undergoing RT. The strengths of this study include the use of an “in-office” easy to use exercise intervention that reduces participant burden, the timing of exercise inception that coincides with RT inception, and use of biomarkers.

g. Future Plans

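### Prior chemotherapy is allowed and recorded before assignment, but the covariate rule usually keeps this plausible prognostic factor out of the model, so a small precision gain is forgone

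*Combined protocol and SAP*

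**What the plan says.** - **Population.** Study Design: "This RCT targets women with breast cancer stages 0-IIIA scheduled to receive RT". The exclusions in Eligibility Criteria include "4) concurrent chemotherapy; (5) distant metastases". Earlier chemotherapy is not excluded and no washout is stated, so women with and without it can both enter.
- **Timing of information.** Under Recruitment, the coordinators "complete baseline and follow-up assessments, including demographic and treatment history, and will make study assignment as below". Table 1 lists "Cancer and Treatment Summary (Appendix D") at screening. Under Randomization, "After completing baseline assessments, eligible participants will be assigned to study arm by a study coordinator". Prior chemotherapy can therefore be known before the envelope is opened.
- **Allocation.** Participants go to exercise "or to the control group using a block randomization scheme". Neither a stratification factor nor a block size is named.
- **Analysis.** The sample size rests on an ANCOVA that adjusts for baseline fatigue. Under Statistical analysis, age is the only covariate named for the change-score ANCOVA. In the linear mixed models, known confounders and other covariates are included only if each is associated, at the 10% level, with study group and also with the outcome.

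**The concern.** The sample may mix women who had chemotherapy before radiotherapy with women who did not. It is plausible, though the documents do not say so, that the two groups follow different fatigue and blood-marker courses over the following weeks. The baseline score captures where a woman starts but not necessarily where she is heading, so part of the difference could remain after baseline adjustment.

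The factor is available at no extra data cost, but the plan makes no firm use of it. The 10% rule works against it: because it requires an association with group, it shuts out a covariate that predicts outcome but happens to be balanced, and that is the usual result of randomisation. What is at stake is some residual variance left in the Aim 1 and Aim 3 comparisons. There is also the prospect of deciding after the fact what to do if an imbalance appears.

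**Working it through.** **Inputs from the documents (Sample size Considerations):** means 42.53 and 37.12, SDs 9.35 and 9.42, correlation 0.64, two-sided alpha 0.05, 40 per arm.

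**1. The plan's own figure.**
- Difference: 42.53 − 37.12 = 5.41.
- Pooled SD: √[(9.35² + 9.42²)/2] = 9.385.
- Residual SD after baseline: 9.385 × √(1 − 0.64²) = 7.21, so residual variance is 52.0.
- n per arm for 90% power, normal approximation: 2 × [(1.960 + 1.282) × 7.21/5.41]² = 37.3, rounded up to 38 (39 with the noncentral t).
- Power at 40 per arm, noncentral t: 91.2%. The stated 40 per arm is reproduced.
- Standard error of the contrast: √(52.0 × 2/40) = 1.61 points.

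**2. Assumptions not in the documents.** Prevalence of prior chemotherapy p = 30-50%. Shift in the week-4 score given baseline, g = 2-5 FACIT-Fatigue points. All figures take 40 analysed per arm, since no dropout allowance is stated.

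**3. Gain from a fixed term.** The factor accounts for p(1 − p)g² of the residual variance.
- Low end: 0.3 × 0.7 × 2² = 0.84, or 0.84/52.0 = 1.6%.
- High end: 0.5 × 0.5 × 5² = 6.25, or 6.25/52.0 = 12.0%.

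| Analysis at 40 per arm | Power |
|---|---|
| Baseline only | 91.2% |
| Factor in model, not stratified | 91.3-93.9% |
| Factor in model, stratified | 91.6-94.2% |

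Scenario by scenario, stratification adds about 0.2-0.4 power points to the model term. With the stratified and adjusted design, the n per arm for 90% power falls from 38 to 33-37.

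**4. How often the 10% rule admits the factor.** Simulation: 6,000 trials per scenario, blocks of 4, 40% prevalence, unstratified.
- g = 4: admitted in 5.3% of trials. g = 2: admitted in 2.6%.
- With g = 4, power was 90.4% with baseline only, 90.4% under the 10% rule and 91.8% with the term always included. Stratified with the term it was 92.6%.
- Under stratification the rule never admitted the factor, because the arms were then balanced on it.
- Simulation error is about √(0.91 × 0.09/6000) = 0.4 points per figure, so small gaps between these figures should not be over-read.

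**5. Chance imbalance.** Hypergeometric, 80 women split 40/40: an imbalance of 20 percentage points or more has probability 8.7% at p = 30%, 11.0% at 40% and 11.7% at 50%. At exactly 20 points the estimate moves by 0.20 × 2 = 0.4 to 0.20 × 5 = 1.0 points. That is 0.4/1.61 = 0.25 to 1.0/1.61 = 0.62 of a standard error.

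**The case against.** A reader might infer that the randomisation is at fault: that leaving a known prognostic factor unstratified biases the trial or costs it its power. The documents do not support that.

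- **Valid as designed.** Blocked allocation without strata is unbiased. A chance imbalance favours either arm equally often, and its contribution is already in the standard error and in the 91.2% power. This stands.
- **Premise inferred.** The text never mentions prior chemotherapy, its share, its timing or its effect on fatigue. The Background says only that nearly all patients report fatigue from treatment. Calling the factor known, or the women recently off chemotherapy, goes beyond the text. This stands; plausible is as far as one can go.
- **Partly handled already.** With 24 of 40 against 16 of 40, the Pearson chi-square gives p = 0.074 and passes the group screen, although Fisher's exact test gives 0.117 and does not. If the outcome association also passed, the factor would enter the mixed model. The covariate list for the change-score ANCOVA is also open-ended. So the plan has some protection against a large imbalance, but this does not recover the routine precision gain when the arms are balanced.
- **Why this factor?** Stage also varies, and the documents do not rank prior chemotherapy above it. The choice is a judgement. It does not rescue a rule that would discard any balanced prognostic factor.
- **No benefit if the factor does not matter.** With g = 0 and no stratification, simulated power was 90.3% without the term and 90.0% with it, so the loss would be negligible.

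**Conclusion.** The concern holds as a minor point about covariate pre-specification. The plan collects treatment history before assignment, allows prior chemotherapy, and then applies a screening rule that would seldom let the factor into the mixed models: about 5% of trials at 40% prevalence and a 4-point effect, fewer if the effect is smaller. Under the assumed ranges, the forgone gain is roughly 0 to 3 power points on a trial that already meets its target. Nearly all of it comes from the model term rather than from stratification. If the true effect given baseline is below 2 points, the gain is close to nothing. The direction of the argument applies equally to the Aim 3 biomarkers, but the documents give no figures from which to size it there.

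**What to change.** Pre-specify prior chemotherapy in the current treatment episode (yes/no), alongside the baseline value, as a fixed term in every Aim 1 and Aim 3 ANCOVA and mixed model, whatever the 10% screen shows. If a mixed model keeps the baseline measurement as a response, include the term's interaction with time, since a main effect alone cannot represent a different course.

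The cost is one model term (one degree of freedom in the ANCOVA), with no new data and no extra patients.

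Stratifying the block sequence on the same factor is optional. It guards against a visible imbalance in a single trial of 80, but needs a second envelope series. The coordinator would have to read the treatment history before choosing the series and could open the wrong one, and final arm sizes may differ by a few women. If stratification is adopted, the stratum must be in the model, which the present 10% rule would prevent.

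### Control-arm activity is not recorded during radiotherapy, so the planned between-arm test of adherence has no control-arm definition or data, and a null result would be hard to interpret

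*Combined protocol and SAP*

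**What the plan says.** All references are to the combined protocol and SAP.

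- **Eligibility Criteria.** The activity recall is used to establish that a woman is sedentary at entry: "less than 60 minutes per week of modest physical activity based on 7-day physical activity recall questionnaire".
- **Assessments, Table 1.** The row "Physical activity recall questionnaire (Appendix E" is marked under Screening and nowhere else. FACIT-Fatigue, FACT-B, the inflammation biomarkers and the vital signs are marked at baseline, T1 and T2.
- **Intervention, Arm 1.** "Participants will record their activity on a daily basis on an exercise log (Appendix H".
- **Intervention, Arm 2.** "Control group participants will be told to maintain their current daily activities and exercise habits for the duration of their treatment". No log or questionnaire is attached to this instruction.
- **Study retention and adherence.** "Adherence is recorded in daily participation logs", and "Logs document participant identification, date, and length of time utilizing the Pedlar device".
- **Statistical analysis, Aim 2.** "We will use the binomial test to compare acceptance and adherence rates between the two intervention arms". The closing paragraph of that section adds: "The GRA will collect log data of the women exercising using the Pedlar device".

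**The concern.** Two gaps follow from the same schedule.

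First, one of the three specific aims concerns adherence, and its planned test needs an adherence rate in each arm. The stated source of adherence data is time on a device that controls are not assigned.

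Second, controls receive an instruction about their activity that nothing in the schedule checks. They have consented to an exercise trial, cannot be blinded to their assignment, and may start to exercise. The contrast is modest: about 75 minutes a week on the device against women who enter below 60 minutes a week. If the fatigue difference came out near zero, the data could not show whether the programme failed, controls became active, or exercise-arm women cut back on other activity. The Future Plans section intends these data to support a larger trial, and that trial would need to know which of these occurred.

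**Working it through.** **Step 1: who has activity data, and when.**

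| | Screening | During radiotherapy | T1 and T2 visits |
|---|---|---|---|
| Exercise arm, on the device | 7-day recall | Daily log of minutes | none beyond the log |
| Exercise arm, off the device | 7-day recall | none described | none described |
| Control arm | 7-day recall | none described | none described |

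**Step 2: what the adherence test needs.** A two-arm comparison needs a count of adherent women and a denominator in each arm. In the exercise arm the log can supply the count once a threshold is set. In the control arm neither a definition nor a source is given.

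**Step 3: reproduce the plan's sample size.** Inputs from Sample size Considerations: means 42.53 and 37.12, SDs 9.35 and 9.42, baseline correlation 0.64, two-sided alpha 0.05, 40 per arm, 90% power.

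- Difference = 42.53 − 37.12 = 5.41.
- Pooled SD = √((9.35² + 9.42²)/2) = 9.385.
- ANCOVA residual SD = 9.385 × √(1 − 0.64²) = 7.211.
- n per arm, normal approximation = 2 × (1.960 + 1.282)² × (7.211/5.41)² ≈ 37.3, so 38. The noncentral F with 1 and 2n − 3 degrees of freedom gives 39.
- At 40 per arm the noncentrality is (5.41/7.211)² × 40/2 = 11.26, and power is 91.2%.

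The plan's 40 per arm at 90% power is reproduced.

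**Step 4: how much contamination could go unseen (assumption, not a document figure).** Suppose a share u of controls takes up exercise and each gains a fraction g of the 5.41-point benefit. The expected difference is then 5.41 × (1 − u × g). Power is by noncentral F at 40 per arm.

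| Uptake u | Difference, full benefit (g = 1) | Power | Difference, half benefit (g = 0.5) | Power |
|---|---|---|---|---|
| 0% | 5.41 | 91.2% | 5.41 | 91.2% |
| 10% | 4.87 | 84.7% | 5.14 | 88.2% |
| 20% | 4.33 | 75.5% | 4.87 | 84.7% |
| 30% | 3.79 | 64.0% | 4.60 | 80.4% |

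**Step 5: what a one-arm adherence estimate would give.** If, for example, 32 of 40 exercise-arm women (80%) were adherent, the Wilson interval has centre (0.8 + 3.841/80)/(1 + 3.841/40) = 0.774 and half-width 1.960 × √(0.8 × 0.2/40 + 3.841/6400)/(1 + 3.841/40) = 0.121. That is about 65% to 90%, precise enough for a pilot aim.

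**The case against.** **The exercise arm is recorded.** A reader might infer that activity goes unmeasured in everyone after screening. The documents do not support that: exercise sessions are supervised and device minutes are logged daily. The gap is control-arm activity and off-device activity.

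**The log, or adherence itself, might cover both arms.** The log sentence refers to participants in general, and Appendices E and H are not in the available text. Adherence could also mean staying in the assigned arm and attending visits, which can be counted in both arms. These readings are possible but weaker. The log sentence sits under Arm 1, and both later mentions tie the logs to use of the device. It is therefore safer to say that control-arm adherence is undefined and has no stated source than that no reading could rescue the test.

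**The power figures do not measure this defect.** This stands. The loss comes from contamination, not from failing to record it, and adding a questionnaire recovers none of it. Full benefit is also the worst case, because a control exercising alone need not gain what a supervised programme gives. The 5.41 points are an observed difference from the team's earlier unpublished study, so they may already contain some dilution.

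**This is a pilot, and tracking controls is a preference.** In part this stands. The abstract promises preliminary evidence, and unrecorded activity does not bias the comparison of the arms as randomised. The Aim 2 test, however, is an inconsistency in the plan itself and not a matter of taste.

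**Conclusion.** The point holds in a limited form. Activity in controls, and off the device in the exercise arm, has no scheduled measure during radiotherapy. The between-arm adherence test therefore lacks a control-arm definition and source and cannot be run meaningfully as written. This rests on the body text and Table 1; an unseen appendix could add a control-arm record, but nothing in the body points to one.

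A reader might go further and conclude that the fatigue comparison is invalid or that the trial is underpowered. Neither follows. The as-randomised comparison is valid, the sample size reproduces, and the power figures show only what assumed contamination could do unnoticed. What is lost is the explanation of a null result and one stated Aim 2 analysis. The change should be made, but the trial's main conclusion does not depend on it.

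**What to change.** 1. In Table 1, add the existing 7-day recall (Appendix E) at T1 in both arms. T2 is optional and would only describe activity after treatment, since the control instruction covers the treatment period.
2. In the Statistical analysis section, replace the between-arm binomial test of adherence with two items:
   - session adherence from the logs in the exercise arm only, as a proportion with a 95% confidence interval and a threshold stated in advance;
   - a between-arm comparison of change in weekly activity minutes from each woman's own screening value to T1, with the control-arm change also reported descriptively as contamination.
3. Keep the as-randomised comparison as the main analysis.

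The 60-minute entry limit should not serve as the definition of control adherence. The instruction is to keep current habits, and a woman who goes from 0 to 55 minutes a week would pass that limit despite a large change.

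The cost is a few minutes per woman at a visit already scheduled, with no change to the sample size. The limits are self-report over a single week and a small chance that asking controls about exercise prompts it.
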